Latent class modeling was used both to reduce the number of covariates used to adjust for baseline factors and to examine possible moderators of the exposure outcome relationship (Table 3). If we were treating each covariate as a potential confounder or as an individual effect modifier, we would need to perform formal imputation of missing data elements of an item that contributes to a latent class or drop patients who had one or more missing items. By contrast, latent class modeling does not require complete data on every factor that contributes to a class. Mixture models generated latent classes and probabilities of class membership for all patients which were used to assign patients to these classes even if some data elements used in the mixture model were missing. This approach assumed missingness completely at random (MCAR), or at least missingness at random given the values of other covariates. In addition, the latent class method allows for the high degree of collinearity among the candidate factors. In short, latent class modeling both accomplished data reduction (too many covariates for adjustment) and facilitated identification and testing of patient subgroup differences in treatment effect.

Statistical power

Estimates of power for longitudinal data must account for the added power of following individuals over time. To estimate power of our somewhat complex design, we resorted to statistical simulations, implemented in Stata v 13 (StataCorp, College Station, TX), in which we varied the correlations of outcome within individual over time. Using the asthma control measure as an example, we estimated that power of a balanced design with 300 evaluable subjects was adequate (from 0.82 to 0.87) to detect a difference between groups of 1/3 of a

standard deviation of asthma control. According to Juniper's work on asthma control, this detectable difference is less than the minimally important clinical difference.^{22,47} Additional simulations, for effect modification, suggested good power (0.9) to demonstrate a greater improvement among low literacy patients with home visitors. For all results, confidence intervals reflect the post hoc power.

Programs and software

Analyses were performed in SAS v9.4 (SAS Institute Cary NC), Stata v 15.0 and 15.1 (College Station Texas), and M Plus v7.0 (Los Angeles CA).

Trial monitoring

An external Data Safety Monitoring Board reviewed progress and data every six months and monitored adverse events and serious adverse events (unexpected ED visits and hospitalizations). Because patients had moderate or severe asthma, it was expected that ED visits and hospitalizations for these and patients' co-morbid conditions would occur but perhaps change as a result to the interventions.

Changes to the original study protocol

There were no substantive changes to the original study protocol. Small changes made it easier for patients to adhere to the protocol. For example, if it were easier for the patient, we went to their home for enrollment. For some patients the first portal training session and the second were given on the same day for those for whom a single training session was more convenient.

REFERENCES

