**Using IT to improve access, communication, and asthma in African American and Hispanic/Latino Adults
NCT 02086565**

June 25, 2018

METHODS AND DATA ANALYSIS

Study Overview

The overall study design has been previously published.¹ We describe methods in full here, and in more detail in the attached appendix (Appendix A). Adults with uncontrolled asthma, generally unfamiliar with the patient portal, were recruited from outpatient primary care and specialty clinics of two health systems that serve predominantly but not exclusively low-income urban neighborhoods. Participants were trained in the use of the portal: Portal Training (PT). Participants were then randomized 1:1 to home visits (HV), from a Community Health Worker (CHW, described below), to encourage use of the portal and to facilitate care coordination or no home visits. The project was approved by the University of Pennsylvania Institutional Review Board and was registered with ClinicalTrials.gov (NCT02086565).

Study design

We chose a randomized controlled trial (**HV + PT versus PT**) because randomization reduces the likelihood of bias from both known and unknown confounders.² The longitudinal design supports baseline measures as within-subject controls and the multicenter recruitment also enhances the generalizability to a diversity of social circumstances.

The choices for the randomized trial, portal training (PT) and home visits (HV), were inspired by the RE-AIM conceptualization framework³ and the need for implementation research.⁴ Implementation of portal training and home visits were hypothesized to improve access and communication resulting in improved patient-centered outcomes including asthma control and asthma-related quality of life.

Those randomized to PT+HV worked with the same CHW who conducted both portal training sessions. At each home visit, the CHW ensured care coordination, including obtaining an asthma action plan that linked patients' home and community with the clinic. The CHW provided standard asthma education, promoted communication with providers, encouraged appointment keeping, and facilitated familiarity with health information technology.

Study setting

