CHWs live in the community and are familiar with the environment; are acceptable to patients; and connect patients to health education, services, and the health care setting.⁵⁻⁷ In our Community Asthma Prevention Program (CAPP), we identified and trained CHWs as lay health educators to provide home asthma education and environmental intervention. Over 20 years, CAPP CHWs have visited 3000+ families with children⁸ in both African American (West Philadelphia) and Hispanic/Latino (North Philadelphia) communities, the same communities for the current project. These CHWs have a high school education or greater with at least three years' work experience and personal knowledge of asthma. They bring their knowledge as a community resident to suggest local resources to meet daily needs. CHWs are able to establish relationships with participants and their families to promote better asthma self-management, connection with community resources, communication with providers and mitigation of asthma triggers. CAPP's CHWs have functioned not only as home visitors, but also as asthma navigators who have been integrated into the health care team, providing a direct link between families and clinicians. Our experience has allowed us to develop an excellent support system including supervision, training, and systems for scheduling visits and data entry.⁹ The retention rate of participating families in CAPP has been above 90%.¹⁰ Home visits for children with asthma often include tailored asthma education and environmental remediation of allergen and irritant environmental exposures.

In the current intervention, each home visit included 1) reinforcement of the use of the portal and 2) care coordination (Table 1). Our activities were unique in utilizing CHWs for home visits for promotion of portal use with the intention of linking the patient to the medical practice, thereby improving patient-physician communication, a known contributor to asthma disparities. The home visits focused on communication and access, the same goals as potentially achievable through portal use.

Table 1. Activities and data collection (DC) for PT+HV and PT groups.

Time	PT+HV	PT
DC- Week 0	Participant meets with a member of the research team for consent, enrollment, randomization, and baseline data collection. This data collector is not the CHW who provides PP1, PP2 or HVs (if participant is randomized to HV).	

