PP1 (within 2 weeks of enrollment)	A CHW demonstrates accessing internet if necessary, ensures patient's internet access and request for an activation code for PP, and demonstrates use of PP with a "test" patient. Participants are shown how to complete 7 tasks and how to ask for on-line help and to read FAQs.	
PP2 (within 2 weeks of enrollment)	Patient activates their PP and goes through exercises with the same CHW, using the PP to obtain and ask for information (the 7 tasks demonstrated at PP1). Participants are again shown how to ask for help & to read FAQs. They are given a printed card with a phone number for the Help Line. They are shown how to access medical information through the PP.	
HV1 (within 2-4 weeks of enrollment)	
Re-Introductions & conversation- CHW is the same CHW who supervised PP1 and PP2. CHW meets patient and family and asks how they are doing. Care Coordination. The CHW:
 
 • asks patient to produce medications and explain doses • asks about smokers in home and offers a QUIT number if needed • reviews participant's baseline environmental survey • asks where emergency medical information is kept, emergency telephone numbers • assists as needed as patient drafts an asthma action plan for review/revision by patient's asthma care provider • asks when next appointment with asthma doctor is & assists with scheduling if necessary • asks about refills needed • asks about patient Care Coordination goals 
CHW reviews use of PP and how to access it and the internet including access to health information resources
 
 • shows how to access asthma education materials with the PP 	Email/phone to patient encouraging sign in to PP.
HV2 (between weeks 4-7)	
CHW inquires how patient and family are doing. THEN CHW and participant:
 
 • review Action Plan and care coordination goals, medications, refills, appointments etc. 
CHW and patient review use of tablet and PP:
 
 • Problems with use • Complete at least 2 tasks with PP • CHW demonstrates how to "google" for information 	Email/phone to patient encouraging sign in to PP.

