*Three literacy measures were used: Asthma Numeracy Questionnaire,³⁹ the Short Test of Functional Health Literacy in Adults,⁴⁰ and Electronic Health Literacy.⁴¹ Electronic health literacy was measured with the eHEALS, the eHealth Literacy Scale, an 8-item measure of knowledge, comfort, and perceived skills at finding and evaluating electronic health information.⁴¹ It has been used in low-income patients.⁴² Each item is measured with a 5-point likert scale and the eHEALS score is the mean of each item.

**The Medical Outcomes Study Social Support Survey.^{43,44}

Our working hypothesis was that patients with comorbidities and with limited computer literacy might (a) not benefit from portal education at all, and (b) might have additional benefit with the home visitor intervention. Further details appear in Appendix A6.

Statistical Analysis plan

Testing within-group effects over the time of the study allowed us to assess the effect of each intervention. In brief, the within-group change in the PT group allowed measurement of PT alone. Subtracting any change over time in the PT+HV group from the PT group allowed estimates of the additional effect of home visits.

Intention to treat approach –primary analysis

The primary analysis was “as randomized” (intent to treat), with the assumption that any dropout visits were missing completely at random (MCAR). The estimand of interest was the difference between the home-visitor versus portal-only groups in the change in outcomes over time. We attempted to use mixed effects models, which make less strong missing at random (MAR) assumptions, with varying success. (Details appear below and in the analysis-specific appendix, Appendix A).

Modeling approach – flexible modeling of time

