(2) "Exclusion restriction". The effect of the assignment to the home visitor arm of the study must influence outcome only through the actual completion of the home visit. A patient would have to react the same in terms of asthma outcome if he or she had been assigned to the home visitor treatment arm or the portal only arm, and had received no home visits. In the context of this study, this key assumption would be violated if the mere assignment to the home visitor led to higher expectations of improved asthma outcome just by learning of the assignment, and diminished expectations upon learning of assignment to the patient portal arm. Owing to the unavoidable fact that the patients could not be blinded to the treatment assignment, a violation of this assumption might be possible. But it might be that both the home-visitor patients and the portal-only patients could have similar expectations of some improvement merely by being recruited to the study and followed over time. A variation on this assumption requires that the patient who is randomized to the home visitor group but who does not schedule or see the home visitor (lack of compliance with the protocol) will receive no benefit from just being assigned to the home visit group. That assumption seems plausible in this setting.

(3) The final assumption, "monotonicity", requires that patients assigned to the portal group did not obtain home visits. Our design satisfied this assumption because only patients assigned to the home visit arm of the study were able to receive home visits. Although this assumption was very likely satisfied, meeting this assumption limits the inference of the effect of the home visitors to the patients with the characteristics of those who actually had the full set of home visits. To be able to generalize the effect of home visits to all patients would require yet an additional assumption – that the effect of treatment is the same across all patient types. We feel that this assumption could not be satisfied because home visits, almost by definition, are not going to produce the same reaction and outcome across a diverse group of patient who

Appendix A10 (continued). Estimating effect of home visitors adjusted for incomplete adherence – A sensitivity analysis.

have sometimes markedly different comorbidities, ages, educations, poverty levels, and home environment.

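### The comparator is portal training plus four scheduled sign-in reminders, not training alone; the stated contrast and Appendix A10 should say so

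*Combined protocol and SAP*

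**What the plan says.** Table 1 enters activities common to both arms once (the two portal training sessions, for example) and splits the rest by column. In the HV1, HV2, HV3 and HV4 rows the PT column reads "Email/phone to patient encouraging sign in to PP". The PT+HV column lists no such contact. Its portal content is delivered inside the visit, for example at HV1: "CHW reviews use of PP and how to access it and the internet including access to health information resources". The section on community health workers says the same of every visit: "each home visit included 1) reinforcement of the use of the portal and 2) care coordination".

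The narrative does not mention the reminders. The Study Overview describes the alternative to home visits as no home visits, and the Study design section names the contrast as HV + PT against PT. The Statistical Analysis plan section then says that "the within-group change in the PT group allowed measurement of PT alone", and that "Subtracting any change over time in the PT+HV group from the PT group allowed estimates of the additional effect of home visits".

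Appendix A10, assumption (2), states the exclusion restriction: a patient must have the same asthma outcome whether "assigned to the home visitor treatment arm or the portal only arm, and had received no home visits". It concedes that this might be violated because patients know their assignment and may form different expectations. No other cause is considered.

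**The concern.** If the comparator arm has a scheduled contact that the home-visit arm lacks, the arms do not differ by home visits alone. The PT change then includes whatever the reminders do, and the between-group difference compares visits with reminders. A null result could be misread as home visits adding nothing to portal training. An improvement within PT could likewise be credited to training alone.

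The same feature bears on the complier analysis. A PT+HV patient who receives no visit is scheduled for no reminder, while a PT patient is scheduled for four. The Mediation section hypothesises that greater portal use leads to better outcomes. On the trial's own causal model, then, reminders could link assignment to asthma control without any visit taking place.

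**Working it through.** **Schedule, from Table 1**

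| Time point | PT+HV | PT |
|---|---|---|
| HV1 | Portal review in person | Email/phone reminder |
| HV2 | Portal review in person | Email/phone reminder |
| HV3 | Portal review in person | Email/phone reminder |
| HV4 | Portal review in person | Email/phone reminder |

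Reminders scheduled: 1 + 1 + 1 + 1 = 4 in PT and 0 in PT+HV.

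**Plan's own figure.** No stated number depends on the reminders. The Statistical power section gives 0.82 to 0.87 for 300 evaluable patients and a difference of 1/3 SD. With 300/2 = 150 per arm and two-sided alpha of 0.05 (assumed; the section states none), power = Φ((1/3)/√(2/150) − 1.960) = Φ(2.887 − 1.960) = 0.823, the lower end. Naming the comparator correctly leaves this unchanged.

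**What the two summaries estimate.** Count improvement as a fall in the asthma control score. Let T be the mean improvement with training and no later contact (natural course included), r the mean extra improvement from reminders, and v the mean extra improvement from assignment to home visits, averaged over all PT+HV patients, visited or not.

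- PT within-group change = T + r. The plan reads it as T.
- PT+HV within-group change = T + v.
- Between-group difference = (T + v) − (T + r) = v − r. The plan reads it as v.

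Both readings are exact only if r = 0. If r > 0, the difference is smaller than the effect of adding visits to training, but it is exactly the effect of visits in place of reminders.

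**Exclusion restriction.** Let r_u be the reminder effect in patients who would receive no visit. Their improvement is T_u if assigned to PT+HV and T_u + r_u if assigned to PT. The restriction needs a difference of zero; the schedule gives −r_u. A10's response model has no term for assigned arm, and portal-only patients enter with adherence and residual both set to zero. They therefore help to define the no-visit regime, and an effect of reminders on them has nowhere else to go.

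**Direction.** In a simple ratio estimator, let a share p of PT+HV be visited, with effects v_c and r_c in those patients:

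[p(v_c − r_c) − (1 − p)r_u]/p = (v_c − r_c) − r_u(1 − p)/p.

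If r_u > 0, this falls below the visits-versus-reminders effect in compliers. A10 uses a modified two-stage residual inclusion model, so the formula shows direction only. The documents give none of r, r_u or p, so no size follows.

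**The case against.** The strongest reply is that nothing is wrong with the design. Visited patients get portal encouragement in person at the same four time points, so a reminder is a reasonable low-intensity counterpart, and choosing such a comparator is legitimate. That stands. A reader might infer that the randomised comparison does not hold; the documents do not support this. Assignment was random and the as-randomised analysis validly compares two strategies. Only the description of the comparator is wrong.

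A reader might also infer that A10 declares the two-arm exclusion restriction plausible. It does not. The sentence ending "will receive no benefit from just being assigned to the home visit group. That assumption seems plausible in this setting" concerns a variation, that an unvisited PT+HV patient gains nothing from assignment. Reminders sent to the PT arm do not contradict that statement, so it need not be replaced. The gap is that A10 names one cause of a possible breach and omits another.

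Nor do the documents show that missed visits were common. A10 reports incomplete adherence and slipped schedules without a frequency. Its non-adherent category includes delayed and partly visited patients, who still received portal reinforcement at the visits they had.

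Finally, Table 1 gives a schedule, not delivery. The Internet access section estimates that half of potential participants had computer access and that only half of those checked email regularly, though phone was also an option. A10 describes adherence partly as staying in contact with staff, so patients who missed visits may also have been hard to reach with reminders. The reminder effect in those patients may be small. This limits any claim about size; it does not make the reading of PT as training alone correct.

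**Conclusion.** The point holds as one of description and interpretation. As scheduled, the contrast is portal training plus home visits against portal training plus four sign-in reminders, and the two interpretive sentences in the Statistical Analysis plan section do not match Table 1. This rests on taking Table 1's columns at face value.

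For A10, the restriction is threatened and unaddressed, not shown to fail: it is breached by this route only if reminders change asthma control, and the documents offer a hypothesis about portal use rather than evidence. If reminders help, the bias is toward a smaller home-visit effect. A numerical bias would have to be built on invented values of the reminder effect and the share visited, so none is given. A10 is also a sensitivity analysis and does not determine the primary result.

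**What to change.** 1. In the Study Overview, Study design and Statistical Analysis plan sections, state the comparator as portal training plus email/phone sign-in reminders. Interpret the between-group difference, including a null, as visits compared with reminders after common training. Interpret the PT within-group change as change under training plus reminders.
2. State whether PT+HV patients who missed visits also received reminders, and which arm received the quarterly calls encouraging portal use that the Home Visit (HV) Protocol section mentions without naming an arm.
3. In A10, assumption (2), name the unequal reminders beside expectations as a possible breach, and describe the complier estimate as possibly conservative for that reason.

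Sending reminders to both arms is no longer an option, since the document reports conduct in the past tense. The cost is a few sentences and a check of contact records. The downside is a slightly narrower conclusion about home visits and about training alone.

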Study sites were chosen to recruit the most diverse group of patients who satisfied enrollment criteria and whose clinical experience was diverse (primary care versus specialist care, different health practices (University of Pennsylvania and Temple). Participating sites included two family medicine, two general internal medicine, two pulmonary, and one allergy-immunology outpatient practice from the University of Pennsylvania Health System (UPHS). Recruiting from these practices in the past had consistently yielded a population that was more than 65% African American and more than 65% female. More than 1000 patients with asthma, prescribed inhaled steroids, and living in low income neighborhoods were identified in initial screening. Because University of Pennsylvania clinics are not in Hispanic/Latino areas of Philadelphia, we recruited and enrolled patients from Hunting Park Adult Medicine, a primary care practice serving mainly Spanish-speaking patients, more than 85% Hispanic/Latino, and with more than 700 patients with asthma on their problem lists.

Participants

We planned to identify 300 adults living in low-income neighborhoods with moderate to severe asthma requiring urgent care and little previous exposure to the portal.

Inclusion criteria: We recruited adults, only one from a household:

- 18 years or older.
- living in a Philadelphia neighborhood in which at least 20% of households have incomes below the federal poverty level.
- having a doctor's diagnosis of asthma.
- prescribed an inhaled corticosteroid-containing medication.
- who required prednisone or had an ED visit or hospitalization for asthma in the past year.
- who had not previously signed in to a portal more than 3 times.
- who were patients in a participating clinic.

Exclusion criteria

Severe psychiatric or cognitive problems (e.g., obvious mania, schizophrenia, significant mental retardation) that would make it impossible to understand and carry out this protocol.

Recruitment

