The IRB-approved consent and all communications were read/spoken in English or Spanish as preferred by the potential participant. Data collection was accomplished by a CHW, called a Data Collector, who did not act as the home visitor if the patient was so assigned. This choice of Data Collector reduced any pressure on the patient to answer in a way to please the researcher CHW. Baseline questionnaires assessed socio-demographics, asthma severity, health literacy, and comorbidities (Table 2). The first and last data collection visits were in person so that spirometry could be measured. For the other data collection times, we offered a phone or email or in-person visit to minimize the burden of and effect on participation in a study. The Data Collector entered responses either directly into a secure, encrypted, web-based database REDCap (Research Electronic Data Capture) or on paper for transfer to REDCap later.³³ Data Collectors used tablets (iPads) equipped with Wi-fi but internet access was difficult at times and CHWs noted many patients were not comfortable with having their information entered onto an iPad.

For each patient we collected their contact information and that of three persons. We also were able to read the electronic record to determine when patients had appointments and to meet them there. Additionally, we wrote letters, visited homes, and left postcards.

Data management

REDCap (<http://www.project-redcap.org/>) allows data attribution and audit capabilities, integrity checks, real-time validation, data storage and backup, and export functions.³⁴

Whenever any response of the patient required elaboration, the interviewer entered comments into this database.

At weekly meetings, the community health workers, project manager, the staff who entered data into REDCap, the project statisticians, and the principal investigators discussed data collection problems. The principal investigator then reviewed all reported adverse events. These meetings then led to the development of project rules for interpreting any of the questions that presented difficulties for patients to answer.

A set of 30 tables stored in the REDCap database contain data from interviews and phone assessments of patients over time (Table 2 and Appendix A1).

Analytical and Statistical Approaches

Patient Portal usage

Portal usage data came from two sources: Penn Medicine and Temple Health. Details on our data management approach to the Portal system appear in Appendix A2.

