Patient activity within Patient Portal Episodes

After combining the two EPIC Portal databases from the two participating institutions, there were 61 activities that appeared for the patients in our sample (Appendix A2, Tables 1 and 2). These activities we then combined into a set that corresponded to the basic Portal usage that participating patients were trained to use (Appendix A2, Table 3). Finally, we calculated the frequency of Portal usage episodes during the duration of the patient's study involvement from randomization to the last data collection (subtracting off any Portal usage that coincided with patient connecting with the community health workers or study personnel). We also calculated the frequency of all portal usage by the rate of usage over time.

Mediation

Mediators explain how the interventions influence asthma outcomes. For this study we designed three candidate mediators to measure communication, access to the health care system, and improved inhaler usage: (1) the rate of portal use over time, (2) appointments kept within 6 months

of a data collection time, and (3) inhaler use according to best practices.³⁰ To determine whether mediation might be present, we first estimated the association between the randomized assignment (portal only versus portal + home visits) and the hypothesized mediator. In the absence of an association, there could be no indirect effect and no mediation. Details appear in Appendices D3 and D4.

(1) **Portal usage** as a potential mediator. Because patient follow-up varied depending on the time from randomization to last data collection interview, portal use was based as a rate or intensity over time. We hypothesized that the home visitor would lead to greater use of the portal, and that with greater portal use, the patient would have better outcomes.

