modifiers leads to underpowered contrasts, excessive reliance on p-value testing, inadequate pre-specification of candidates and their rationale, and no attention to multiple comparisons.³⁷ To address these criticisms, we grouped candidate measures into several clearly pre-specified themes from which profiles or latent classes are derived. We implemented a latent class analysis for each group of candidate measures to distinguish profiles of common responses to the set of variables.^{37,38} Then the degree of effect modification of the association of the intervention (home visitors) and the key outcome (asthma control) was estimated for each candidate modifier group by testing interactions between the candidate moderator variable and the randomization indicator. For those candidate effect modifiers that approached conventional levels of statistical significance, we estimated the intervention effect and 95% confidence intervals for each level of the effect modifier. The nine pre-specified candidate effect modifier groupings appear in Table 3. Details appear in Appendix A6.

Table 3. Relevant patient subgroups for targeting the initiative and their data elements.

Relevant subgroup	Data Elements
(1) Primary language	Primary language is Spanish
(2) Primary care vs specialty practices	Internal medicine or family medicine versus allergy-immunology or pulmonary
(3) Age	18-39 years, 40-49 years, \geq 50 years
(4) Skills that would support use of portal and asthma self-management	Numeracy* Literacy* Education Computer literacy* Inhaler technique
(5) Social Community barriers	Food or clothing inadequacy MOS Social Support** Violence
(6) Trust of medical personnel	Patient portal preserves privacy
(7) Depression and chronic disease load	Depression Diabetes Hypertension High cholesterol Obesity Cancer Current Smoker
(8) Asthma severity	Hospitalizations ED visits Intubation Years taking ICS Prednisone (Days/week)
(9) Home environment	Crowding at home (number of rooms, number of people at home) Been without housing in last 6 months Utilities shut off in the last 6 months Times moved in last 12 months Exposure to second hand smoke

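### A home-visit effect that differs between Hunting Park and Penn would show up as modification by Spanish language and, in part, by type of care, so neither label can be read alone.

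*Combined protocol and SAP*

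**What the plan says.** Table 3 lists nine candidate modifier groupings intended to help target the program. The first is "Primary language is Spanish"; the second is "Internal medicine or family medicine versus allergy-immunology or pulmonary".

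Study setting explains the mix of sites. Penn supplies four primary care practices (two in family medicine, two in general internal medicine) and three specialty practices (two pulmonary, one allergy-immunology). One more practice was added: "Because University of Pennsylvania clinics are not in Hispanic/Latino areas of Philadelphia, we recruited and enrolled patients from Hunting Park Adult Medicine". It is described as "a primary care practice serving mainly Spanish-speaking patients, more than 85% Hispanic/Latino". It is the only non-Penn practice named. The same section names Temple as the other health system, so Hunting Park is taken to be the Temple site.

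Appendix A6 tests modification with Wald tests of the three-way interaction of time, intervention and candidate modifier, at p < 0.1. Separate regressions at each level of the modifier follow. The Model form paragraph in the main text and Appendix A7 bring in clinic as a stratification factor, and Appendix A8 lists clinic and Spanish language among its fixed effects. No clinic-by-intervention term and no Penn-only analysis is described. The subgroup text does not mention that language and site overlap.

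**The concern.** By design, Spanish primary language is closely tied to one practice and so to one health system. In the second subgroup, the primary care level contains that practice and the specialty level does not.

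A clinic main effect absorbs differences between sites in the level of asthma control. It does not absorb a difference between sites in the effect of home visits, which is what a treatment interaction measures. If home visits did more, or less, at Hunting Park for local reasons, the language test would pick up most of that and the practice-type test part of it.

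A local difference is possible. Appendix A10 accepts that eight home visitors may have delivered somewhat different versions of the intervention, and the Home Visit Protocol says that visit reports went on paper through clinic staff. Extending the program to Spanish speakers at other clinics, or to primary care in general, assumes that the labelled characteristic drives the effect. A site effect would not carry over.

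**Working it through.** **The plan's own figure.** The only power figure for asthma control is 0.82 to 0.87, for 300 evaluable patients and a difference of 1/3 SD. With 150 per arm and two-sided alpha 0.05 (assumed), z = (1/3)/√(2/150) − 1.96 = 0.93, which gives power 0.823. For the mean of four follow-ups minus baseline with correlation 0.3 (assumed), the SD is √((1 + 3×0.3)/4 + 1 − 2×0.3) = 0.935, which gives 0.870. Both ends are attainable. The figure concerns the overall comparison; none is given for the language or practice-type tests.

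**Assumed inputs.** The documents give no enrolment by site or language. The ranges used are:
- Hunting Park share of the sample, h: 10% to 30%
- Spanish-primary share at Hunting Park, s: 50% to 90%
- Spanish-primary share at Penn, p: 0% to 5%
- primary care share of Penn patients, q: 40% to 70%
- difference between sites in the home-visit effect: 0.30 points, with no true effect of language or type of care

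**Language.** Arms are balanced within clinic, so the spurious interaction is 0.30 × [P(Hunting Park | Spanish) − P(Hunting Park | not Spanish)]. A weighted regression with clinic and language main effects, arm, and arm-by-language gave the same values.
- Lowest (h = 0.10, s = 0.50, p = 0.05): 0.050/0.095 = 0.526 and 0.050/0.905 = 0.055, so 0.30 × 0.471 = 0.14.
- Highest (h = 0.10, s = 0.90, p = 0): 1 and 0.010/0.910 = 0.011, so 0.30 × 0.989 = 0.30.

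In these ranges Hunting Park holds 53% to 100% of Spanish-primary patients, or 85% to 100% if p is at most 1%.

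**Practice type.** No specialty patient is at Hunting Park, so the spurious interaction is 0.30 × h/[h + (1 − h)q].
- Lowest (h = 0.10, q = 0.70): 0.10/0.73 = 0.14, giving 0.04.
- Highest (h = 0.30, q = 0.40): 0.30/0.58 = 0.52, giving 0.16.

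**Cost of a Penn-only contrast.** In SD units, the standard error of the interaction is √(4/n₁ + 4/n₂), where n₁ and n₂ are the numbers in primary and specialty care.
- h = 0.10, q = 0.70: n₂ = 81; n₁ falls from 219 to 189; standard error 0.260 to 0.266, up 2%.
- h = 0.30, q = 0.40: n₂ = 126; n₁ falls from 174 to 84; standard error 0.234 to 0.282, up 20%.

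**Can language be separated from site?** Not at Penn: with p at most 1% there are about 0 to 3 Spanish-primary Penn patients, and with 5% about 11 to 14. Within Hunting Park, take a generous 100 patients, 80% Spanish-primary, and an SD of 1.0 (all assumed). That is 40 Spanish-primary and 10 other patients per arm, so the standard error is √(2/10 + 2/40) = 0.50. The sign of this estimate would agree with the all-site result about 50% of the time with no language effect, and about 73% of the time with a true 0.30 (Φ(0.30/0.50)).

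**The case against.** The strongest reply is that randomization was stratified by clinical site. The home-visit effect within Spanish speakers, or within primary care, is therefore a randomized comparison whatever the mix of sites. This stands. A reader might infer that the two subgroup analyses are invalid or cannot be used; the documents do not support that.

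Second, a reader might infer that type of care cannot be separated from health system. It can: Penn alone has four primary care and three specialty practices. The all-site contrast is only partly mixed, and the assumed shift of 0.04 to 0.16 points is small beside an all-site interaction standard error of about 0.23 to 0.28 SD.

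Third, a reader might blame different portals. The evidence is weak. The plan does say "Portal usage data came from two sources: Penn Medicine and Temple Health", but it also says "After combining the two EPIC Portal databases from the two participating institutions", and participants were trained on the same seven tasks. No passage states that staffing or clinic processes differed by site, so a site difference is possible but not shown.

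Fourth, it is tempting to say that almost all Spanish speakers were at Hunting Park. That is a reasonable inference, not a documented count. The 85% figure is ethnicity in the practice population, not primary language among enrolled patients.

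These replies narrow the point to attribution. They do not remove it: the planned tests cannot tell a site difference from a language difference, and the plan does not say so.

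**Conclusion.** The point holds as a limit on interpretation. A difference in the home-visit effect between Hunting Park and Penn would load heavily onto the language interaction and partly onto the practice-type interaction, because clinic is adjusted for only as a main or stratifying term. The true size is unknown. The ranges scale directly with the assumed 0.30 points and rest on assumed enrolment shares; the Temple affiliation of Hunting Park is inferred. The primary analysis is unaffected. This is a low-cost improvement to two exploratory analyses.

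**What to change.** **Type of care.** Keep the pre-specified all-site interaction. Beside it, report the same interaction within the Penn practices only: family and general internal medicine against pulmonary and allergy-immunology. Attribute a difference to type of care only on the Penn-only estimate and its interval.

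**Language.** Report the cross-tabulation of language by site. Label the all-site result as language and site combined. Show the Spanish-versus-English estimate within Hunting Park with its interval, as descriptive only. Do not use agreement in sign as grounds for attributing the effect to language.

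**Cost.** One extra model run, one table, a descriptive estimate and a relabelling, with no new data. The Penn-only intervals are somewhat wider, and the claim that can be made about language is weaker.
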